- Grade 4 hematologic toxicities (attributed to study drugs) defined as:
  - Grade 4 thrombocytopenia (platelets  $< 25$  K/ $\mu$ L)
  - Grade 4 neutropenia (absolute neutrophil count (ANC)  $< 0.5$ )
- Grade 3 thrombocytopenia or neutropenia that results in a  $> 4$  day delay in any romidepsin dose in cycle 1.
- One week or greater delay in initiating cycle 2 day 1 due to continued drug-related toxicity.

At the time of enrollment the patients will be identified as representing three cohorts based upon disease subtype: 1) B-cell lymphoma 2) multiple myeloma 3) PTCL. Each disease specific cohort will enroll 15 patients. We plan to accrue 38 patients into the phase IIa portion including those treated at the MTD of the phase Ib portion. The assessment of toxicity and efficacy will be performed within the entire cohort evaluable at MTD. A preplanned exploratory analysis of the toxicity and efficacy of the disease specific cohorts will also be performed. Efficacy measures which will be determined include ORR, CBr (for myeloma), TTR, DOR, and EFS. ORR is defined as the percentage of patients achieving a best response of CR/CRu, very good partial response (VGPR--myeloma only), or PR at any disease assessment time point. CBr is defined as CR, VGPR, PR or MR (minimal response) in myeloma patients. TTR is defined as the time or number of cycles between study registration and documentation of first response (CR/Cru, VGPR, or PR). DOR is defined as the time or number of cycles between documentation of first response and progression, change of therapy, death, or date of last contact (if still alive without progression). EFS is defined as the time between study registration and documented progression, change in therapy, or death if no progression was observed.

[figure not shown]

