## **10.7 Follow-Up**

Patients, who discontinue treatment for any reason, will be followed for 1 month or until resolution of all treatment related AEs or initiation of alternate cancer therapy, whichever is longer. At treatment discontinuation, patients will undergo a safety assessment approximately 1 month after the last dose of protocol therapy. In addition, off study evaluations per the end of study assessments will be done.

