 Lymphoma: CT including at least the chest, abdomen and pelvis or PET/CT is required for response (systemic B and T-cell lymphoma patients only) assessment. A bone marrow will only be repeated to confirm a complete response if previously known to be involved. Cutaneous T-cell lymphoma patients will have imaging at baseline and (CTCL) will have an mSWAT (Appendix I) performed monthly for the first three cycles and then at each response assessment timepoints (end of cycle 4, 6 and thereafter at the end of every third cycle). In CTCL patients, imaging will be repeated if appropriate (patients with known nodal or visceral disease) every other cycle. Sezary panel in patients with Sezary syndrome. Cutaneous lymphoma patients without nodal or visceral disease will have imaging repeated only to confirm a complete response. After cycle 12, patients on continuous therapy may be imaged as clinically indicated, at the discretion of the treating physician. At discontinuation of therapy, end of study response assessments – including imaging – should be performed.

Serum/urine protein electrophoresis, serum/urine immunofixation, quantitative immunoglobulins, and serum free light chains are required if appropriate for (multiple myeloma patients only) response assessment. A bone marrow will only be repeated if to confirm a complete response. Patients with non-secretory myeloma will have the bone marrow assessment repeated if they have been otherwise clinically stable (i.e. without new lytic lesions, soft-tissue plasmacytomas or hypercalcemia). A skeletal survey is allowed to rule out bone lesions for evaluation of disease progression and to confirm a complete response in nonsecretory multiple myeloma. PET/CT should be performed at screening and to confirm responses in patients with soft tissue plasmacytomas.

 An additional safety assessment will be done 28 days (+/- 2 days) following the last dose of protocol therapy.

 If romidepsin is omitted on day 8 per dose reduction algorithm (Table 4) then hematologic and electrolyte assessments are not required.

Response assessment will be performed at the end of cycles 2, 4, and 6. Thereafter, response assessment will occur at the end of every third cycle (9,12,15, etc.) until disease progression or removal from study. Myeloma patients will have their disease assessed after each cycle.

 +/- 3 days

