True toxicity rate	5%	10%	15%	20%	25%	30%	35%	40%	50%
Dose reduction prob.	0.000	0.000	0.001	0.004	0.016	0.056	0.118	0.243	0.632

18 months after the final patient is enrolled and after 80% of patients, MSKCC will analyze disease status, serious adverse events and survival for all patients.

Secondary objectives of this study aim at examining many clinical endpoints (see Sections 4 and 12 for detailed definitions). Overall response rate (ORR) and clinical benefit rate (CBr) for MM patients, complete response rate, very good partial response/partial response rate will be summarized using proportions and confidence intervals will be provided. Time to response, duration of response and event free survival will be analyzed by routine survival analysis tools such as Kaplan-Meier estimation or competing risks method. In this portion of the study, all three disease subtypes (B-cell lymphoma, multiple myeloma, PTCL) will be grouped together including those from the phase Ib that were treated at MTD. Note that the response criteria are different among the disease subtypes (see Section 12.0). To preliminarily collect the data, subset analyses will also be conducted to evaluate the ORR, TTR, DOR, and EFS for each disease subtype.

To further investigate activity of this regimen in patients with acute T-cell leukemia/lymphoma, an additional cohort of 6 patients will be added to the phase IIa portion of the study. When the true response rate is 30% or above, the probability that none of the 6 patients will respond is less than 0.12. Subset analyses will be conducted to evaluate the ORR, TRR, DOR, and EFS for each disease subtype.

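### Duration of response is censored at last contact, not at the last disease assessment, so it can include progression-free time that nobody verified; the upward bias ranges from negligible to material, depending on follow-up.

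*Combined protocol and SAP*

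**What the plan says.** Section 4.1 runs DOR from first documented response to "progression, change of therapy, death, or date of last contact (if still alive without progression". Last contact is thus the censoring date for a responder with no event. The same section gives EFS its events but no censoring date: "EFS is defined as the time between study registration and documented progression, change in therapy, or death if no progression was observed". Section 14.0 says that "duration of response and event free survival will be analyzed by routine survival analysis tools such as Kaplan-Meier estimation" or a competing-risks method, and adds no censoring rule.

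The Table 7 legend sets the assessments. Response is assessed at the end of cycles 2, 4 and 6, after which "response assessment will occur at the end of every third cycle (9,12,15, etc.) until disease progression or removal from study"; myeloma is assessed every cycle. For lymphoma imaging, "After cycle 12, patients on continuous therapy may be imaged as clinically indicated, at the discretion of the treating physician". A final assessment is required: "At discontinuation of therapy, end of study response assessments", including imaging, should be performed.

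Section 13.1 ends treatment when either drug is stopped, whatever the reason. Under Section 10.7, patients who stop "will be followed for 1 month or until resolution of all treatment related AEs or initiation of alternate cancer therapy", with the longest of these governing. That section adds a safety assessment at about 1 month and the end-of-study evaluations, but no repeated disease assessment. Finally, at a point timed 18 months after the last enrolment, Section 14.0 says that "MSKCC will analyze disease status, serious adverse events and survival for all patients".

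**The concern.** Last contact shows that a patient is alive. It shows that the response persists only if someone looked. Here contact can outlast assessment in two ways:

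- A responder may stop without progression and start no recorded new therapy. Contact can then continue through open-ended follow-up or the late status analysis, with no further assessment required.
- A patient still on treatment may be censored between assessments.

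In both cases the Kaplan-Meier method treats the interval as observed progression-free time, so the error can only lengthen DOR. Section 4.1 offers the phase IIa efficacy results as background for a possible later subtype-specific phase II study, and Section 14.0 plans DOR by subtype. With at most 15 patients in each main cohort, responders will be few, and one or two long unverified tails can move a subtype curve.

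**Working it through.** The plan states no expected median, precision or sample size for DOR, so there is no figure to reproduce. The check is textual, followed by an illustration of size.

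**1. Does any text override last contact?** No. Section 14.0 names methods only, and neither the Table 7 legend nor Section 10.7 sets a censoring date.

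**2. How long can the unverified gap be?**
- On treatment, lymphoma after cycle 6: 3 cycles × 28 days = 84 days. After cycle 12, imaging has no fixed interval.
- After stopping: about 1 month if contact ends at the safety visit. It can be much longer under Section 10.7 or the late analysis. The documents give no typical value.

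**3. How often is the status wrong?** Assume exponential time to progression with median m, and a responder who stops free of progression and is not assessed again. The chance of true progression within a gap of g months is 1 − 0.5^(g/m).

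| Gap g (months) | m = 17 | m = 6 |
|---|---|---|
| 1 | 1 − 0.5^(1/17) = 4% | 1 − 0.5^(1/6) = 11% |
| 6 | 22% | 50% |
| 12 | 39% | 75% |
| 18 | 52% | 87% |

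The 17 months is the single-agent romidepsin PTCL figure in Section 3.1.3.2; the 6 months is assumed.

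**4. Effect on the median.** This is a simulation of 200,000 responders per setting, with non-informative stopping, continuous assessment until stopping and no progression detected afterwards. With a true median of 17 months and 20% stopping early, last-contact censoring gives 17.1, 18.0, 18.8 and 19.4 months for gaps of 1, 6, 12 and 18 months. Across true medians of 6, 12 and 17 months and 10-40% stopping, the overstatement is 0.1-0.5 months for a 1-month gap, 0.3-2.9 for 6 months, 0.3-5.5 for 12 months and 0.3-7.9 for 18 months. Last-assessment censoring returns the true median within simulation error.

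**5. Effect on 12-month DOR when some later progression is captured.** All inputs except the 84-day interval are assumed:
- true median 8 months, so the true value is 0.5^(12/8) = 35%;
- 20% or 30% of responders given an exponential stopping time with mean 5 months;
- median survival of 24 months after progression;
- data cut 16-40 months after response.

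| Situation after stopping | Censored at last contact | Censored at last assessment |
|---|---|---|
| Contact ends at 1 month | 38.1% | 37.2-37.6% |
| 80% of progression captured | about 39-40% | 37-38% |
| 50% captured | 41-43% | 37-38% |
| None captured | 44-47% | 37-38% |

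The excess is 1 point or less in the first row, about 1.5-2.5 points at 80% capture (1.4 to 3.2 across runs coded slightly differently), and about 6-9 points with no capture. About 2 points of the distance from the true 35% come from detecting progression only at 84-day visits, and these appear under both rules. With a true median of 12 months (true value 50%), the results are about 53-60% against 52%.

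These 12-month figures reflect early stoppers only. With a cut at 16 months or later, an on-treatment patient's last assessment falls after month 12 (16 months less 84 days is about 13.2 months).

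**6. Does last-assessment censoring settle it?** Not alone. The last-assessment column censors every early stopper at stopping and ignores later events. Suppose later deaths and captured progressions count as events, while event-free stoppers are censored at their last assessment. The estimate is then 39-40% at zero capture, because undetected progression surfaces only at death. At full capture it is 36-37%, against 37-38% under simple censoring, because late events count while late event-free time does not.

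**The case against.** The case against a stronger claim is good, and most of it stands.

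- A reader might infer that patients merely known to be alive are counted as progression-free. The text does not say so: last contact applies only to patients alive without progression. What remains is that no assessment is required to establish that condition.
- A reader might take follow-up to stop at 1 month. Section 10.7 applies the longest of its limits, one of which is the start of alternate cancer therapy. Change of therapy is already a DOR event. The post-treatment problem is therefore confined to responders who stop without progression, later progress undetected, and have no new therapy recorded before last contact.
- A reader might call the late analysis a survival check. It also covers disease status, though the plan does not say how that is established.
- A reader might quote 44-47% against a true 35% as the bias. That is the zero-capture extreme, and part of the difference is the visit interval. The 8-month median is also below the single-agent romidepsin medians in Section 3.1.3 (14.9 and 17 months).
- A reader might say that EFS has the same error. Section 4.1 gives EFS no censoring date, so this is a gap.
- Precision is low. If 15 to 20 of about 44 patients respond (assumed), the binomial standard error near 40% is √(0.4 × 0.6/20) = 11 to √(0.4 × 0.6/15) = 13 points, larger than the bias in any row. That limits the practical weight of the point. It does not justify a rule whose error always runs in one direction.

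**Conclusion.** The point holds in limited form. Section 4.1 fixes a censoring date that can credit unverified progression-free time, nothing elsewhere corrects it, and the bias is upward. It affects responders who stop without progression and have no recorded new therapy, and patients censored in on-treatment gaps between assessments.

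The size cannot be read from the documents. Under the assumptions of step 5 with an 8-month median, it runs from 1 percentage point or less at 12 months when contact ends soon after stopping to about 6-9 points when no later progression is captured. It is small if few responders stop early or later events are well recorded. DOR is a secondary, descriptive endpoint with no decision threshold, and the MTD and toxicity objective is unaffected. The direction is certain; the magnitude is illustrative.

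**What to change.** In Sections 4.1 and 14.0:

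1. For patients without an event, censor DOR at the last adequate disease assessment showing no progression.
2. State how progression, death or new therapy occurring after the last assessment or after discontinuation is handled: for example, whether it counts as an event or the patient is censored at the last assessment. Apply the rule to all patients alike; step 6 of the working shows that the choice moves the estimate in either direction.
3. Report last-contact censoring as a sensitivity analysis.
4. State the same censoring rule for EFS.

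The cost is a few sentences. Assessment dates are already collected, and no visit, sample size or error rate changes. The downside is that DOR becomes slightly shorter and some follow-up time is lost to earlier censoring.

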## 4.2 Intervention

All patients will be treated with romidepsin intravenously on days 1, 8, and 15 and lenalidomide orally on days 1-21 of a 28-day cycle. The dose will be determined by the cohort they are registered into. Once a MTD is determined this dosing level will be used for the phase IIa portion. Cycles will be continued as above until the patients wishes to be removed from the study, unacceptable toxicity develops, disease progression, treating physician recommends removal, or termination of study occurs.

## 5.0 THERAPEUTIC/DIAGNOSTIC AGENTS

### **5.1 REVLIMID®**

REVLIMID® (lenalidomide), a thalidomide analogue, is an immunomodulatory agent with anti-angiogenic properties. The empirical formula for lenalidomide is C13H13N3O3, and the gram molecular weight is 259.3. The chemical name is 3-(4-amino-1-oxo 1,3-dihydro -2H-isoindol-2-yl) piperidine-2, 6-dione and it has the following chemical structure:

Lenalidomide is off-white to pale-yellow solid powder. It is soluble in organic solvent/water mixtures, and buffered aqueous solvents. Lenalidomide is more soluble in organic solvents and low pH solutions. Solubility was significantly lower in less acidic buffers, ranging from about 0.4 to 0.5 mg/ml. Lenalidomide has an asymmetric carbon atom and can exist as the optically active forms S(-) and R(+), and is produced as a racemic mixture with a net optical rotation of zero.

The mechanism of action of lenalidomide remains to be fully characterized. Lenalidomide possesses immunomodulatory and antiangiogenic properties. Lenalidomide inhibited the secretion of pro-inflammatory cytokines and increased the secretion of anti-inflammatory cytokines from peripheral blood mononuclear cells. Lenalidomide inhibited cell proliferation with varying effectiveness (IC50s) in some but not all cell lines. Of cell lines tested, lenalidomide was effective in inhibiting growth of Namalwa cells (a human B cell lymphoma cell line with a deletion of one chromosome 5) but was much less effective in inhibiting growth of KG-1 cells (human myeloblastic cell line, also with a deletion of one chromosome 5) and other cell lines without chromosome 5 deletions. Lenalidomide inhibited the expression of cyclooxygenase-2 (COX-2) but not COX-1 *in vitro*.

#### **5.1.1 Absorption:**

Lenalidomide, in healthy volunteers, is rapidly absorbed following oral administration with maximum plasma concentrations occurring between 0.625 and 1.5 hours post-dose. Co-administration with food does not alter the extent of absorption (AUC) but does reduce the maximal plasma concentration (Cmax) by 36%. The pharmacokinetic disposition of lenalidomide is linear. Cmax and AUC increase proportionately with increases in dose. Multiple dosing at the recommended dose-regimen does not result in drug accumulation.

Pharmacokinetic analyses were performed on 15 multiple myeloma patients treated in the phase I studies. Absorption was found to be rapid on both Day 1 and Day 28 with time to maximum blood levels ranging from 0.7 to 2.0 hours at all dose levels (5mg, 10mg, 25mg, and 50mg). No plasma accumulation was

observed with multiple daily dosing. Plasma lenalidomide declined in a monophasic manner with elimination half-life ranging from 2.8 to 6.1 hours on both Day 1 and 28 at all 4 doses. Peak and overall plasma concentrations were dose proportional over the dosing range of 5mg to 50mg. Exposure (AUC) in multiple myeloma patients is 57% higher than in healthy male volunteers.

### **5.1.2 Pharmacokinetic Parameters:**

#### **Distribution:**

In vitro (C)-lenalidomide binding to plasma proteins is approximately 30%.

#### **Metabolism and Excretion:**

The metabolic profile of lenalidomide in humans has not been studied. In healthy volunteers, approximately two-thirds of lenalidomide is eliminated unchanged through urinary excretion. The process exceeds the glomerular filtration rate and therefore is partially or entirely active. Half-life of elimination is approximately 3 hours.

#### **Supplier(s)**

Celgene Corporation will supply Revlimid® (lenalidomide) to study participants at no charge through Celgene's Revlimid Risk Evaluation and Mitigation Strategy™ (REMS) (formerly known as RevAssist® Program).

#### **Dosage form**

Lenalidomide will be supplied as capsules for oral administration.

#### **Packaging**

Lenalidomide will be shipped directly to patients. Bottles will contain a sufficient number of capsules for one cycle of dosing.

#### **Labeling**

Lenalidomide supplies are dispensed in individual bottles of capsules. Each bottle will identify the contents as study medication. In addition, the label will bear Celgene's name, quantity contained and the standard caution statement as follows: "Caution: New drug - Limited by Federal law to investigational use." Lenalidomide should not be handled by FCBP unless wearing gloves.

The study drug label must be clearly visible. Additional labels must not cover the Celgene label.

#### **Storage**

Lenalidomide should be stored at room temperature away from direct sunlight and protected from excessive heat and cold.

## Special Handling Instructions

Females of childbearing potential should not handle or administer lenalidomide unless they are wearing gloves.

## Unused study drug supplies

[figure not shown]
Celgene will instruct the Investigator on the return or destruction of unused study drug. If any study drug is lost or damaged, its disposition should be documented in the source documents. Study drug supplies will be retained at the clinical site pending instructions for disposition by Celgene. Patients will be instructed to return empty bottles or unused capsules to the clinic site.

### 5.1.3 Prescribing Information

Lenalidomide (Revlimid®) will be provided to research subjects for the duration of their participation in this trial at no charge to them or their insurance providers. Lenalidomide will be provided in accordance with the Celgene Corporation's Revlimid REMS® program. Per standard Revlimid REMS® program requirements, all physicians who prescribe lenalidomide for research subjects enrolled into this trial, and all research subjects enrolled into this trial, must be registered in, and must comply with, all requirements of the Revlimid REMS® program. **Only enough lenalidomide for one cycle of therapy will be supplied to the patient each cycle.**

## 5.2 Romidepsin

Romidepsin (ISTODAX®) is a unique bicyclic depsipeptide originally isolated from *Chromobacterium violaceum* strain 968. [Ueda H, 1994] Romidepsin is an antineoplastic agent that has been identified as a novel HDAC inhibitor. Romidepsin has been shown to induce hyperacetylation of histones and other nonhistone protein species resulting in a variety of phenotypic changes, induction of the upregulation of gene transcription, G1 and G2/M arrest of the cell cycle, morphological reversion of transformed cells, cell growth inhibition, apoptotic cell death, and inhibition of angiogenesis.

The molecular formula of romidepsin is  $C_{24}H_{36}N_4O_6S_2$ , its molecular weight is 540.71, and its chemical name is: (1S,4S,7Z,10S,16E,21R)-7-ethylidene-4,21-bis(1-

methylethyl)-2-oxa12,13-dithia-5,8,20,23-tetraazabicyclo[8.7.6]tricos-16-ene-3,6,9,19,22-pentone.

In both *in vitro* and *in vivo* systems, romidepsin has been shown to elicit a range of biological activities, including HDAC inhibition, induction or repression of gene expression, cell cycle arrest, differentiation, cell growth inhibition, apoptotic cell death, morphological reversion of transformed cells, and inhibition of angiogenesis. The manner in which romidepsin and other HDAC inhibitors exert their biological effects has not been fully elucidated. The current view is that these agents inhibit, to a greater or lesser extent, the activity of Class I (HDACs 1, 2, 3, 8), Class II (HDACs 4, 5, 6, 7, 9, 10), and Class IV (HDAC 11) HDACs, causing chromatin remodeling and altered gene expression, which results in biological effects that are deleterious to tumor cell growth and survival. There is a growing body of evidence that HDAC inhibitors can also target substrates other than histones and that the posttranslational modification of cellular proteins by acetylation may play an important role in the biological activities of HDAC inhibitors.

